Planned interim analysis was performed with a data cut-off of 29-Nov-2017 after approximately 30 patients in the well-differentiated NET group had undergone the first 3 radiological assessments, had shown disease progression, or had discontinued efficacy follow-up for any other reason. The full analysis set included 95 patients in the well-differentiated NET group (30 patients in the thoracic cohort, 33 patients in the pancreatic cohort and 32 patients in the GI cohort) and 21 patients in the poorly-differentiated GEP-NEC group. Median duration (range) of follow-up (from treatment to data cut-off date) was 5.3 months (3.7-8.5 months) and 3.6 months (2.3-4.6 months) in the well-differentiated NET and poorly-differentiated GEP-NEC groups, respectively. With this limited follow up, the overall response rate (ORR) per RECIST 1.1 based on central radiology review was 3.2% in the well-differentiated NET group (10.0 % in the thoracic cohort, 0% in the pancreatic cohort, and 0% in the GI cohort) and 0% in the poorly-differentiated GEP-NEC group.

Safety analysis excluded events occurring 30 days after study treatment discontinuation. The most common adverse events (AEs) ($\geq 15\%$ in all patients; all grades) reported at the time of the interim analysis were fatigue (34.7% in well-differentiated NET cohort and 14.3% in poorly-differentiated GEP-NEC cohort), pyrexia (25.3% and 9.5%, respectively), diarrhea (20.0% and 14.3%, respectively), nausea (16.8% and 28.6%, respectively), abdominal pain (18.9% and 9.5%, respectively), and constipation (16.8% and 14.3%, respectively). The most common grade 3/4 AEs (≥ 2 of patients in each group) in well-differentiated NET cohort were abdominal pain and anemia (each in 4 patients), hypertension (3 patients), and fatigue and dyspnoea (each

in 2 patients). Abdominal pain, cough and back pain (each in 2 patients) were the most common grade 3/4 AEs in poorly-differentiated GEP-NEC cohort. No fatal SAEs were reported at the time of this analysis.

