5.2 Inclusion criteria

Patients eligible for inclusion in this study have to meet **all** of the following criteria:

1. Written informed consent must be obtained prior to any screening procedures
2. Adult males or females \geq 18 years at screening.
3. Pathologically confirmed, advanced (unresectable or metastatic):

- Well-differentiated (G1 /2) based on local pathology report, non-functional neuroendocrine tumor of GI, pancreatic or thoracic (including lung and thymus) origin.
 - Poorly-differentiated GEP-NEC based on local pathology report
4. No active symptoms related to carcinoid syndrome during the last 3 months prior to start of study treatment.
5. Patients must have received prior treatment for advanced disease:
- Well-differentiated NET group:
 - a. Thoracic (lung and thymus origin) cohort:
 - Thymus origin: at least one prior systemic therapy according to investigator's choice
 - Lung origin: at least one prior systemic therapy is required, which must include everolimus.
 - b. GI cohort: at least two prior systemic regimens, which must include everolimus. Prior systemic therapies may include: somatostatin analogs, PRRT, and/or chemotherapy.
 - c. pNET cohort: at least two prior systemic regimens, which must include everolimus and/or sunitinib. Prior systemic therapies may include: somatostatin analogs, PRRT and/or chemotherapy.
- Note: For well-differentiated NET, prior treatment with interferon alpha is allowed provided that it is not the last treatment received prior to study entry.
- Poorly-differentiated GEP-NEC group: at least one prior chemotherapy regimen according to Investigator's choice.
6. Radiological documentation of disease progression :
- Well-differentiated NET group: Disease progression while on/or after the last treatment, and this progression must have been observed within 6 months prior to start of study treatment (i.e. maximum of 24 weeks from documentation of progression until study entry). Disease must show evidence of radiological disease progression based on scans performed not more than 12 months apart.
 - Poorly-differentiated GEP-NEC group: Disease progression while on or after prior treatment.
7. At least one measurable lesion assessed by CT and/or MRI according to RECIST 1.1.
Note: Any lesions which have been subjected to percutaneous therapies or radiotherapy should not be considered measurable, unless the lesion has clearly progressed since the procedure.

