6.4 Concomitant medications

6.4.1 Permitted concomitant therapy

In general, concomitant medications and therapies deemed necessary for the supportive care (e.g. such as anti-emetics, anti-diarrhea) and safety of the patient are allowed except those prohibited in [Section 6.4.3](#). The following list includes permitted concomitant therapies:

- Medications to prevent or treat nausea or vomiting.
- Anti-diarrheal medications (e.g., loperamide) for patients who develop diarrhea.
- Pain medication to allow the patient to be as comfortable as possible.
- Localized radiotherapy and treatment with bisphosphonates for pre-existing, painful bone/liver metastases is permitted. The radiotherapy must be listed on the CRF.
- Immunosuppressive agents to treat suspected irAEs.
- Nutritional support or appetite stimulants (e.g. megestrol).
- Oxygen therapy and blood products or transfusions.
- Limited-field palliative radiotherapy may be allowed as concomitant therapy. Such local therapies administered during the study treatment must be listed on the CRF.

- Inactivated vaccines.
- The patient must be told to notify the investigational site about any new medications he/she takes after the start of the study drug. All medications (other than study drug) and significant non-drug therapies (including physical therapy, herbal/natural medications and blood transfusions) administered during the study must be listed on the Concomitant Medications.

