7.2 Assessment types

7.2.1 Efficacy assessments

Tumor response will be assessed locally and centrally according to the Novartis guideline version 3.2 ([Appendix 1](#)) based on RECIST 1.1 ([Eisenhauer et al 2009](#)) and irRECIST ([Appendix 2](#)). The imaging assessment collection plan is presented in [Table 7-2](#). Details of the central review process will be described in the independent review charter.

Imaging data will be centrally collected and checked for quality by an imaging Contract Research Organization (CRO) designated by Novartis. The results of the central evaluations will be used for primary analysis purposes. The local investigator's assessment will be used for treatment decision making as described in [Section 7.2.4](#).

Information regarding prior interventions (e.g., radiotherapy), pre-existing radiographic findings that mimic metastatic disease at baseline/screening and prior interventions should be transmitted to the imaging CRO via the Baseline Clinical Form along with the screening images for review by the independent radiologist. Sites must ensure the data entered on the form is consistent with the data entered in the clinical database.

Information regarding cytology results should be transmitted to the imaging CRO via the Cytology Form for all visits, when applicable, for review by the independent radiologist. Sites must ensure the data entered on the form is consistent with the data entered in the clinical database.

After primary analysis cut-off date (10-Aug-2018), medical imaging data and information regarding cytology results will no longer be collected and transmitted to the imaging Contract Research Organization (CRO) for central tumor response evaluation. Tumor response will be assessed locally by investigator, according to RECIST 1.1 ([Appendix 1](#)) and irRECIST ([Appendix 2](#)).

Table 7-2 Imaging Assessment Collection Plan

Procedure	Screening (Day -28 to Day -1)	During Treatment/Follow-up (+/- 7 day window)

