10.4.2 Statistical hypothesis, model, and method of analysis

No formal hypothesis testing will be conducted. The objective of the study is to demonstrate the antitumor activity of PDR001 as measured by ORR.

The response rate within each group on the FAS population with 95% two-sided confidence interval (exact method) will be computed.

Group 1: Well-differentiated NET

The results in this group will be considered a success if both of the following conditions are met:

1. a clinically relevant response rate of at least 10% is observed
2. 95% two-sided CI for ORR excludes the value 3%.

With 90 treated patients enrolled, the success corresponds to at least 9 responders observed (i.e. a response rate of 10% with [4.7; 18.1] 95% CI).

In the absence of historical comparator in this setting, response rates reported in placebo arms of previous randomized phase III studies in earlier lines of treatment can be considered as a valid historical reference for ORR in well-differentiated NET ([Table 1-1](#)). A 95% two-sided CI excluding the value 3% will ensure that the clinically relevant observed response rate is significantly higher than expected placebo response rate.

Group 2: Poorly-differentiated GEP-NEC

This group will enroll approximately 20 patients. Estimates of the ORR along with 95% two-sided CI will be presented. Additionally, the interval probabilities for the true ORR lying within the intervals stated below will be computed.

- 0 - <3% unacceptable efficacy
- 3% - <10% limited efficacy
- 10% - <20% moderate efficacy
- $\geq 20\%$ clinically relevant efficacy

For this analysis a prior distribution for the parameter of interest, ORR, must be specified. For the current study, the prior clinical assumption for PDR001 in the selected patient population is used in order to derive a minimally informative unimodal Beta prior distribution that reflects the level of uncertainty around ORR before starting the current trial ([Neuenschwander et al 2008](#)). The prior mean ORR is set to be equal to 15% and the parameters of the minimally informative Beta prior distribution of ORR have been set up as follows:

- $a/(a+b) = 0.15$

- $a = 0.176$
- $b = 1.0$

At the primary analysis, this prior distribution will be updated with observed ORR data and probabilities that the true ORR lies within the above intervals will be reported.

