10.8 Sample size calculation

Group 1: Well-differentiated NET

In the absence of an established control treatment, ORR reported in the placebo arms of studies reported in [Table 1-1](#) can serve as a reference in the well-differentiated NET group. A 3% ORR is therefore considered as a reasonable reference while an improvement up to 10% is considered as clinically meaningful in this patient population.

Total sample size of 90 patients was chosen such that with an observed 10% response rate, the corresponding 95% CI excludes the value 3%.

Approximately thirty patients will be recruited in each cohort NET cohort: pancreatic, GI and thoracic.

Operating characteristics in the well-differentiated NET group are given in [Table 10-1](#). A sample size of 90 patients ensures a 90% probability of success if the true ORR is 15%.

Table 10-1 Operating characteristics for the full population of well-differentiated NET group

True response rate	Probability of observing 10% or more responders at the end of the study
10%	0.55
11%	0.67
12%	0.77
13%	0.84
14%	0.90
15%	0.94

[figure not shown]
In addition, [Table 10-2](#) shows the probability of observing at least 3 responders in a cohort with 30 patients under the assumption of true response rate of 10-20% in this cohort.

Table 10-2 Probability of observing at least 3 responders in a cohort with more than 10% true response rate

True response rate in a cohort	Probability of observing 3 or more responders in a cohort with 30 patients at the end of the study
10%	0.59
12%	0.72
14%	0.81
16%	0.88
18%	0.93
20%	0.96

Group 2: Poorly-differentiated GEP-NEC

Approximately 20 patients will be enrolled in the poorly-differentiated GEP-NEC group. The operating characteristics are shown in [Table 10-3](#) and [Table 10-4](#). With the planned sample size the probability to observe at least moderate efficacy ($\geq 10\%$ ORR) is more than 80% if the true ORR is 15%. Posterior probability of a true ORR of at least moderate efficacy was computed for different scenarios assuming a minimally informative prior with Beta distribution and the

following parameters: $a=0.176$, $b=1$. Posterior probability of a true ORR to be $\geq 10\%$ ORR is more than 70% if 3 responders are observed in 20 patients.

Table 10-3 Operating characteristics for the poorly-differentiated GEP-NEC group

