Situation F: New cancer therapy given: the handling of this situation must be specified in detail in the protocol. However, option (1) (ITT) is the recommended approach; events documented after the initiation of new cancer therapy will be considered for the primary analysis i.e. progressions and deaths documented after the initiation of new cancer therapy would be included as events. This will require continued follow-up for progression after the start of the new cancer therapy. In such cases, it is recommended that an additional sensitivity analysis be performed by censoring at last adequate assessment prior to initiation of new cancer therapy.

Option (2), i.e. censoring at last adequate assessment may be used as a sensitivity analysis. If a high censoring rate due to start of new cancer therapy is expected, a window of approximately 8 weeks performed after the start of new cancer therapy can be used to calculate the date of the event or censoring. This should be clearly specified in the analysis plan.

In some specific settings, local treatments (e.g. radiation/surgery) may not be considered as cancer therapies for assessment of event/censoring in PFS/TTP/DoR analysis. For example,

palliative radiotherapy given in the trial for analgesic purposes or for lytic lesions at risk of fracture will not be considered as cancer therapy for the assessment of BOR and PFS analyses. The protocol should clearly state the local treatments which are not considered as antineoplastic therapies in the PFS/TTP/DoR analysis.

The protocol should state that tumor assessments will be performed every x weeks until radiological progression irrespective of initiation of new antineoplastic therapy. It is strongly recommended that a tumor assessment is performed before the patient is switched to a new cancer therapy.

Additional suggestions for sensitivity analyses

Other suggestions for additional sensitivity analyses may include analyses to check for potential bias in follow-up schedules for tumor assessments, e.g. by assigning the dates for censoring and events only at scheduled visit dates. The latter could be handled by replacing in [Table 3-2](#) the “Date of last adequate assessment” by the “Date of previous scheduled assessment (from baseline)”, with the following definition:

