2.5.1 Primary endpoint

ORR is defined as the proportion of patients with best overall response (BOR) of complete response (CR) or partial response (PR) according to RECIST 1.1 (see Appendix 1 of the study protocol). ORR will be calculated within each group based on the FAS using BIRC review of tumor assessment data. Patients with only non-measurable disease at baseline will be part of the analysis and will be included in the numerator only if a complete response was observed. Tumor assessments performed before the start of any further antineoplastic therapy (i.e. any additional secondary antineoplastic therapy or surgery) will be considered in the assessment of BOR. Limited-field palliative radiotherapy administered as concomitant therapy per protocol will not

be considered as new antineoplastic therapy. Localized radiotherapy and treatment with bisphosphonates for pre-existing, painful bone/liver metastases is permitted.

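### The plan does not say how a target lesion irradiated on study counts towards response, so radiation shrinkage can be scored as a PDR001 response in the primary ORR

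*SAP*

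**What the plan says.** The primary objective is the antitumor activity of PDR001 as a single agent, measured by confirmed ORR per BIRC.

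- **Radiotherapy on study.** Protocol 6.4.1 says: "Localized radiotherapy and treatment with bisphosphonates for pre-existing, painful bone/liver metastases is permitted. The radiotherapy must be listed on the CRF". It lists limited-field palliative radiotherapy as a separate permitted item. Protocol 6.4.4 repeats the localized form but records it on an antineoplastic-therapy (radiotherapy) CRF page.
- **Which scans count.** SAP 2.5.1 uses assessments made before any further antineoplastic therapy or surgery. Limited-field palliative radiotherapy will not "be considered as new antineoplastic therapy. Localized radiotherapy and treatment with bisphosphonates for pre-existing, painful bone/liver metastases is permitted". Appendix 1, section 3.2.10, says that "palliative radiotherapy given in the trial for analgesic purposes or for lytic lesions at risk of fracture will not be considered as cancer therapy" when BOR and PFS are assessed.
- **Irradiated lesions at entry.** Protocol 5.2 (criterion 7): "Any lesions which have been subjected to percutaneous therapies or radiotherapy should not be considered measurable", with an exception for lesions that have clearly progressed since. Protocol 7.2.2 has the same rule and exception for prior radiotherapy.
- **Irradiated lesions after entry.** I found no rule in either document.
- **What the central reader receives.** Protocol 7.2.1 sends the imaging CRO, with the screening images, "Information regarding prior interventions (e.g., radiotherapy), pre-existing radiographic findings that mimic metastatic disease at baseline/screening". It describes no transfer of radiotherapy given later. It refers to an independent review charter for details of the central read.

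**The concern.** At entry the plan accepts that radiotherapy makes a lesion unreliable for judging drug effect, and it does not apply that principle after entry. Liver metastases can be target lesions. So can lytic or mixed bone lesions with a measurable soft-tissue component (Appendix 1, 2.1.1). If one is irradiated and shrinks, the fall in the sum of diameters is credited to PDR001. There is no control arm in which the same effect would show, and the error can only raise ORR.

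DoR, TTR and irORR use the same assessments. DCR is largely unaffected, because a patient moved from SD to PR was already counted as controlled.

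A second problem is ambiguity. The CRF page for localized radiotherapy treats it as antineoplastic, while SAP 2.5.1 appears to exempt it. Two programmers could derive different BORs for the same patient.

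**Working it through.** **1. Does the written rule produce a response?**

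- Every baseline target lesion is followed at each evaluation (Appendix 1, 2.3).
- PR is a fall of at least 30% in the sum of diameters from baseline (Appendix 1, Table 2-1).
- A target response of UNK arises only if a lesion is not assessed or is assessed by a different method (same table). Irradiation triggers neither, and irUNK in Appendix 2 is similar.
- Confirmation needs a second determination at least 4 weeks later, before progression (Appendix 1, 3.1).
- The planned ORR sensitivity analyses (Protocol 10.4.4, SAP 2.5.4) cover unconfirmed responses and local review, not radiotherapy.

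So the visible text allows the false response.

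**2. How large must the irradiated lesion be?** With other lesions unchanged, the shrinkage needed is 0.30 / (lesion's share of the baseline sum).

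| Share of baseline sum | Shrinkage needed for PR |
|---|---|
| 100% | 30% |
| 75% | 40% |
| 60% | 50% |
| 50% | 60% |
| 40% | 75% |
| 30% | 100% |

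Below 30% the lesion cannot produce a PR alone. Illustration: targets of 50 and 30 mm (irradiated share 50/80 = 62.5%), with the first halved. The sum goes from 80 to 55 mm, and 55/80 − 1 = −31%, a PR.

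**3. The plan's own success rule.** Protocol 10.4.2: "With 90 treated patients enrolled, the success corresponds to at least 9 responders observed". The exact (Clopper-Pearson) interval for 9/90 is 4.68% to 18.14%, which reproduces the stated [4.7; 18.1].

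**4. The rule at the actual size.** Protocol 1.2.1.2: "The full analysis set included 95 patients in the well-differentiated NET group". Ten percent of 95 is 9.5, so 10 responders are needed. The additional efficacy analysis reported 7.

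| Responders of 95 | ORR | Exact 95% CI | At least 10%? | Excludes 3%? |
|---|---|---|---|---|
| 7 | 7.4% | 3.01–14.6 | no | yes |
| 8 | 8.4% | 3.7–15.9 | no | yes |
| 9 | 9.5% | 4.4–17.2 | no | yes |
| 10 | 10.5% | 5.2–18.5 | yes | yes |

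The 10% condition is the binding one. From 7, three extra responses are needed; two are not enough.

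**5. Sensitivity to an assumed frequency.** The documents give no rate. Let f be the assumed chance that a true non-responder is scored as a responder because of radiotherapy. The apparent rate is p + (1 − p)f, and success is P(X ≥ 10) with n = 95.

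| f | True ORR 10% | True ORR 3% |
|---|---|---|
| 0 | 0.482 | 0.0006 |
| 0.1% | 0.493 | 0.0007 |
| 0.5% | 0.540 | 0.0018 |
| 1% | 0.595 | 0.0045 |

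**6. GEP-NEC group.** No success threshold applies, but single responses weigh heavily. Going from 1 to 2 responders of 20 moves the posterior probability of a true ORR of at least 10% from 15.8% to 44.0% (Protocol Table 10-4).

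**The case against.** The case on the other side is substantial, and most of it stands as a limit on size and certainty.

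- **The exemption is only partly explicit.** SAP 2.5.1 names limited-field palliative radiotherapy and says of the localized form only that it is permitted. Appendix 1 reaches painful liver lesions only through its wording on analgesic purpose. A reader might infer that both documents expressly exempt localized bone/liver radiotherapy. They do not, and that is a reason to clarify the text.
- **The charter is unseen.** It may tell central readers how to treat an irradiated lesion, or provide for on-study treatment data to reach them. The point therefore concerns what the protocol and SAP allow, not what the readers did.
- **The route is narrow.** Up to five target lesions are chosen across the involved organs, blastic bone lesions are non-measurable, and the response must be confirmed without progression elsewhere. The 50/30 mm example is a favourable one.
- **The threshold probability is easy to misread.** The chance of exactly 9 true responders of 95 is 13.6% at a true ORR of 10%. A reader might take that as the chance of a changed conclusion. It is only the chance of sitting one below the threshold; a false response must also occur.
- **Consequences are limited.** Enrolment is closed and single-agent development in NET has ended.

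None of this supplies the missing rule. The derivation of the primary endpoint belongs in the SAP, whatever the charter says.

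**Conclusion.** The gap is real. Followed as written, the protocol and SAP can count radiation shrinkage of a dominant target lesion as a confirmed PR in the single-agent ORR, and the SAP leaves unclear whether localized bone/liver radiotherapy ends the BOR window.

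The direction is upward; the size is unknown and probably small. If 0.1% to 1% of true non-responders were affected (an assumption), the chance of success at a true ORR of 10% would rise by about 1 to 11 percentage points. At the 3% reference rate it would stay below 0.5%.

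The conclusion rests on there being no rule in the charter. The 7/95 count precedes the primary cut-off and may change. A reader might infer that one or two radiation responses would alter the trial's conclusion. From the reported 7/95 that is not so, because three more responses are needed. Nor do the documents show that any reported response followed radiotherapy.

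**What to change.** 1. State in SAP 2.5.1 whether localized radiotherapy to bone/liver metastases is exempt from the BOR cut-off. Reconcile this with Protocol 6.4.1 and 6.4.4 and Appendix 1, section 3.2.10.
2. State that a target lesion irradiated on study cannot contribute to a first CR or PR from that date. PD stays assignable, and responses confirmed earlier are kept.
3. Report ORR and irORR with and without this rule. The minimum is a pre-specified sensitivity analysis that counts as non-responders those whose response began after radiotherapy to a target lesion.
4. Identify cases from the CRF radiotherapy records, with case review where the site is ambiguous. The documents do not show that the CRF distinguishes two lesions in one organ, so a purely programmed match may not be enough.

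The cost is SAP wording, one extra analysis and perhaps manual review of a few patients. ORR may be lower, and under the strict rule some true responses in non-irradiated lesions may be lost, which is why both versions should be shown. If no target lesion was irradiated, the result is unchanged and the report can say so. Whether radiotherapy is permitted is not affected.
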